2.9.5.1. Immunogenicity Analyses

The primary analysis population for immunogenicity will be the PP Immunogenicity Set, unless otherwise specified. The primary objective of this study is to use the immunogenicity response to infer efficacy in participants receiving mRNA-1010.

Immune responses, as measured by GMT and seroconversion rate in the mRNA-1010 group based on Day 29 HAI titers, will be compared to that in participants receiving the active comparator for all 4 strains.

Rate of seroconversion is defined as the proportion of participants with either a prevaccination HAI titer <1:10 and a postvaccination titer $\ge1:40$ or a prevaccination HAI titer $\ge1:10$ and a minimum 4-fold rise in postvaccination HAI antibody titer.

An ANCOVA model will be carried out. The model will include the log-transformed HAI titers at Day 29 as the dependent variable, treatment group as the fixed variable, log-transformed baseline HAI titers as a fixed covariate, adjusting for the stratification factors. The GLSM and its corresponding 95% CI results in log-transformed scale estimated from the model will be back-transformed to obtain these estimates in the original scale, as an estimate of the GMT. GMR, estimated by the ratio of GLSM and the corresponding 2-sided 95% CI will be provided to assess the treatment difference. The corresponding 2-sided 95% CI of GMR will be provided to assess the difference in immune response between the mRNA-1010 group compared to the active comparator group at Day 29. For each strain, the noninferiority of GMT will be considered demonstrated if the lower bound of the 95% CI of the GMR is >0.667 based on a noninferiority margin of 1.5.

The number and percentage of participants with seroconversion at Day 29 will be provided with 2-sided 95% CI using the Clopper-Pearson method. To compare the seroconversion rates between the treatment groups, the Miettinen-Nurminen's method will be used to calculate the 95% CI for the difference in seroconversion rates. The difference in seroconversion rate at Day 29 with the corresponding 95% CI will be provided. For each strain, the noninferiority of seroconversion rate will be considered demonstrated if the lower bound of the 95% CI of the seroconversion rate difference is >-10% based on a noninferiority margin of 10%.

The primary analyses will be repeated using the Immunogenicity Set as a supplementary analysis.

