2.5.3.1. Analysis of Primary Endpoints

 GMT as measured by HAI against 4 vaccine-matched influenza virus A and B strains at Day 29

The GMT will be calculated using the following formula:

$$GMT = 2^{\left\{\frac{\sum_{i=1}^{n} \log_2(t_i)}{n}\right\}}$$

where, for n participants, t_i is the immunogenicity titer measurement for participant i.

An ANCOVA model will be carried out. The model will include the log-transformed HAI titers at Day 29 as the dependent variable, treatment group as the fixed variable, log-transformed baseline HAI titers as a fixed covariate, adjusting for the stratification factors. The GLSM and its corresponding 95% CI results in log-transformed scale estimated from the model will be back-transformed to obtain these estimates in the original scale, as an estimate of the GMT.

The GMR for mRNA-1010 vs. active comparator, estimated by the ratio of GLSM and the corresponding 2-sided 95% CI will be provided to assess the treatment difference and calculated by back-transforming of the difference estimated from the ANCOVA model. The corresponding 2-sided 95% CI of GMR will be provided to assess the difference in immune response between the mRNA-1010 group compared to the active comparator group at Day 29. For each strain, the noninferiority of GMT will be considered demonstrated if the lower bound of the 95% CI of the GMR is >0.667 based on a noninferiority margin of 1.5.

Descriptive statistics (n, median, min, max) will also be provided for the GMT of HAI titers with corresponding 95% CI at each timepoint. The 95% CIs will be calculated based on the t-distribution of the log-transformed values then back transformed to the original scale for presentation. In addition, the GMT with corresponding 95% CI will be plotted at each time point respectively.

• Proportion of participants reaching seroconversion at Day 29 as measured by HAI

The number and percentage of participants with seroconversion at Day 29 will be provided with 2-sided 95% CI using the Clopper-Pearson method. To compare the seroconversion rates between the treatment groups, the Miettinen-Nurminen's method will be used to calculate the 95% CI for the difference in seroconversion rates at Day 29. For each strain, the noninferiority of seroconversion rate will be considered demonstrated if the lower bound of the 95% CI of the seroconversion rate difference is > -10% based on a noninferiority margin of 10%.

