3.3.4. Randomization

Randomization will be performed using an IRT. Approximately 3000 participants will be randomly assigned to treatment in this study in a 1:1 ratio to 1 of 2 treatment groups to receive either a single dose of mRNA-1010 or a single dose of a licensed SD seasonal influenza vaccine (Fluarix Quadrivalent, Table 7). Randomization will be stratified by previous flu season (since September 2022) vaccination status (Received; Received from mRNA-1010-P302, Not received).

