3.5.3.1. Analysis of Primary Endpoints

- GMT as measured by HAI against 4 vaccine-matched influenza virus A and B strains at Day 29 (noninferiority testing)
- Proportion of participants reaching seroconversion at Day 29 as measured by HAI (noninferiority testing)

See Section 2.5.3.1 for details.

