3.5.3.4. Analysis of Secondary Endpoints

• GMT as measured by HAI against vaccine-matched influenza virus A strains at Day 29 (superiority testing)

Upon successful demonstration of noninferiority for Part B, superiority of mRNA-1010 relative to a licensed SD seasonal influenza vaccine (Fluarix Quadrivalent) against vaccine-matched influenza A strains (A/H1N1 and A/H3N2) at Day 29 will be tested at a two-sided $\alpha = 0.025$ level. The same ANCOVA model for primary immunogenicity analysis will be applied. The superiority of GMT in participants who received mRNA-1010 compared to GMT in participants who received Fluarix Quadrivalent will be demonstrated by the lower bound of the 97.5% CI of the GMR ruling out 1 (lower bound > 1).

• Proportion of participants reaching seroconversion at Day 29 as measured by HAI against vaccine-matched influenza virus A strains (superiority testing)

If superiority has been demonstrated based on GMT for vaccine-matched influenza A strains, the SCR of the vaccine-matched influenza A strains at Day 29 between the vaccination groups will be compared. The Miettinen-Nurminen's method will be used to calculate the 97.5% CI for the difference in SCRs. The superiority of SCR will be considered demonstrated if the lower bound of the 97.5% CI of SCR difference is > 0.

ModernaTX, Inc. mRNA-1010-P303

• GMT as measured by HAI against vaccine-matched influenza virus B strains at Day 29 (superiority testing)

Upon successful demonstration of superiority (either one or both hypotheses) for vaccinematched influenza A strains, superiority of mRNA-1010 relative to a licensed SD seasonal influenza vaccine (Fluarix Quadrivalent) against vaccine-matched influenza B strains (B/Victoria and B/Yamagata) at Day 29 will be tested:

- If both GMT and SCR hypotheses for vaccine-matched influenza A strains are successful, testing for vaccine-matched influenza B strains will be performed at a two-sided $\alpha = 0.025$ level.
- \circ If only one of GMT and SCR hypotheses for vaccine-matched influenza A strains is successful, testing for vaccine-matched influenza B strains will be performed at a two-sided α =0.0125 level.

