4.3.4. Randomization

Randomization will be performed using an IRT. Approximately 3000 participants will be randomly assigned to treatment in this study in a 1:1 ratio to 1 of 2 treatment groups to receive either a single dose of mRNA-1010 or a single dose of a licensed HD seasonal influenza vaccine (Fluzone HD Quadrivalent, Table 9). Randomization will be stratified by the previous flu season (since September 2022) vaccination status (Received, Received from mRNA-1010-P302.; Not received).

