Estimand Description	Immune response to influenza measured as GMT of vaccine- matched anti-HA level as measured by HAI assay on Day 29 in adults aged at least 18 years inclusive and less than 65 years who receive IP administration and complied with immunogenicity blood sampling to have a baseline and Day 29 antibody assessment without significant protocol deviations impacting immune response.	Immune response to seasonal influenza measured as GMT of vaccine-matched anti-HA level as measured by HAI assay on Day 29 in adults aged at least 18 years or inclusive and less than 65 years who receive IP administration irrespective of any significant protocol deviations impacting immune response and complied with immunogenicity blood sampling to have a baseline and Day 29 antibody assessment as measured by HAI assay.
Target Population	Adults aged at least 18 years inclusive and less than 65 years who receive the assigned IP administration, complied with immunogenicity blood sampling to have a baseline and Day 29 antibody assessment as measured by HAI assay after the IP administration, and have no significant protocol deviations impacting the key or critical data.	Adults aged at least 18 years inclusive and less than 65 years who receive any IP administration and complied with immunogenicity blood sampling to have a baseline and Day 29 antibody assessment as measured by HAI assay.
Endpoint	GMT of anti-HA levels on Day 29	As per Estimand 1a.
Treatment Conditions	mRNA-1010 vs. active comparator (Fluarix Quadrivalent)	As per Estimand 1a.
Population-Level Summary	Immune response to seasonal influenza defined as GMT of anti- HA level as measured by HAI assay using an ANCOVA model on the log-transformed tiers on Day 29, with the vaccination group as the fixed variable, adjusted for stratified previous flu vaccination status used for randomization and log-transformed baseline tiers.	As per Estimand 1a.
Intercurrent Event Strategy		

IcEv1 (early discontinuation or unrelated death)	Principal stratum	Principal stratum	
IcEv2 (alternative influenza vaccine)	Principal stratum	Treatment policy	
IcEv3 (COVID-19 vaccine)	Principal stratum	Treatment policy	
IcEv4 (prohibited medications)	Principal stratum	Treatment policy	
IcEv5 (early infection)	Principal stratum	Treatment policy	
IcEv6 (wrong vaccination)	Principal stratum	Treatment policy	

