Target Population	Adults aged at least 18 years inclusive and less than 65 years who receive the assigned IP administration, complied with immunogenicity blood sampling to have a baseline and Day 29 antibody assessment after the IP administration, and have no major protocol deviations impacting the immune response.	Adults aged at least 18 years inclusive and less than 65 years who receive any IP administration and complied with immunogenicity blood sampling to have a baseline and Day 29 antibody assessment.
Endpoint	Seroconversion rate difference of antibody measured by HAI assay on Day 29.	As per Estimand 2a.
Treatment Conditions	mRNA-1010 vs. active comparator (Fluarix Quadrivalent)	As per Estimand 2a.
Population-Level Summary	Immune response to influenza defined as seroconversion rate difference of antibody using Miettinen-Nurminen's method.	As per Estimand 2a.
Intercurrent Event Strategy		

IcEv1 (early discontinuation or unrelated death)	Principal stratum	Principal stratum	
IcEv2 (alternative influenza vaccine)	Principal stratum	Treatment policy	
IcEv3 (COVID-19 vaccine)	Principal stratum	Treatment policy	
IcEv4 (prohibited medications)	Principal stratum	Treatment policy	
IcEv5 (early infection)	Principal stratum	Treatment policy	
IcEv6 (wrong vaccination)	Principal stratum	Treatment policy	

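### Parts B and C: the seroconversion comparisons use a Miettinen-Nurminen interval with no strata, although randomisation and the GMT model use previous-season vaccination status

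*SAP*

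**What the plan says.** SAP 3.3.4 (Part B) states that "Randomization will be stratified by previous flu season (since September 2022) vaccination status", with three levels: received, received from mRNA-1010-P302, not received. SAP 4.3.4 has the same factor for Part C.

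The two halves of the coprimary family treat this factor differently.

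- **GMT.** SAP 2.5.3.1 adjusts the ANCOVA for the stratification factors. Tables 18 and 19 (SAP 7.8) describe the model as "adjusted for stratified previous flu vaccination status used for randomization and log-transformed baseline tiers".
- **SCR noninferiority.** SAP 2.5.3.1, applied by 3.5.3.1 and 4.5.3.1, says "the Miettinen-Nurminen's method will be used to calculate the 95% CI for the difference in seroconversion rates at Day 29". Protocol 2.9.5.1, applied by 3.9.5.1 and 4.9.5.1, is worded almost identically.
- **SCR superiority.** SAP 3.5.3.4 says "The Miettinen-Nurminen's method will be used to calculate the 97.5% CI for the difference in SCRs". Section 4.5.3.4 refers Part C back to it.
- **SCR estimand.** Tables 18 and 19 give the summary as "defined as seroconversion rate difference of antibody using Miettinen-Nurminen's method".

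None of the SCR passages mentions strata or weights. Vaccination status otherwise enters the SCR analysis only through subgroup analyses that may be conducted (SAP 3.5.3.3 and 4.5.3.3), and these do not alter the confirmatory interval.

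**The concern.** Stratified 1:1 randomisation balances the arms within each stratum, so differences in SCR between strata drop out of the treatment comparison. An unstratified interval computes its variance from the overall rates and still counts those differences as noise. If previously vaccinated participants seroconvert at a different rate, the interval is wider than it needs to be.

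SCR is where power is scarcest. The overall noninferiority powers (98% in Part B, 93% in Part C) equal the SCR powers, against at least 99% for GMT. Stated SCR superiority power is 61–63% in Part B and 41–43% in Part C. A missed A-strain SCR result also carries forward: under SAP 3.5.3.4, the B strains are then tested at two-sided 0.0125 instead of 0.025.

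**Working it through.** **Inputs from SAP 3.3.3 and 4.3.3.** n = 1275 per arm; margin 10 points; one-sided 0.025 (z = 1.960). Noninferiority SCRs, mRNA-1010 vs comparator: Part B 58/59% (A) and 48/49% (B); Part C 58/60% and 48/50%. Superiority SCRs: Part B 64/59% and 54/49%; Part C 64/60% and 54/50%, at two-sided 0.025 (z = 2.241).

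**1. Reproduce the plan's figures.** Let Vm = [pt(1−pt) + pc(1−pc)]/n and d = pt − pc. Per-strain power is Φ((d + 0.10)/√Vm − 1.960). The four strains are multiplied as if independent.

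- Part B, A strain: Vm = (0.2436 + 0.2419)/1275, √Vm = 0.01951, power = Φ(0.09/0.01951 − 1.960) = 99.6%. B strain: 99.5%. All four: **98.2%** (stated 98%).
- Part C, A strain: √Vm = 0.01948, power = Φ(0.08/0.01948 − 1.960) = 98.4%. B strain: 98.1%. All four: **93.3%** (stated 93%).
- Superiority, Φ(d/√Vm − 2.241): 63.9% and 61.3% (Part B), 43.7% and 41.4% (Part C), against stated 63, 61, 43 and 41%.

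The stated powers follow from an unstratified calculation.

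**2. Effect of strata.** Stratum shares and SCR by stratum are not in the documents, so these are assumptions: not received / received / received from P302 of 50/40/10% or 30/50/20%, with SCR lower by a common gap g in both previously vaccinated strata and in both arms. With w the share not previously vaccinated, the true variance is Vs = Vm − 2w(1−w)g²/n.

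- Interval width relative to what is needed: √(Vm/Vs)
- True one-sided level of the unstratified interval: Φ(−1.960·√(Vm/Vs))
- Unstratified noninferiority power: Φ((d + 0.10 − 1.960√Vm)/√Vs)
- Stratified noninferiority power: Φ((d + 0.10)/√Vs − 1.960)

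For superiority, replace d + 0.10 by d and 1.960 by 2.241.

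*Example: Part C, A strain, g = 0.20, w = 0.5.* n·Vs = 0.4836 − 0.0200 = 0.4636, √Vs = 0.01907. Width ratio = √(0.4836/0.4636) = 1.021. Unstratified power = Φ((0.08 − 0.03817)/0.01907) = 98.6%; stratified = Φ(0.08/0.01907 − 1.960) = 98.7%. The B strain goes from 98.3% to 98.5%, and all four from 93.9–94.0% to 94.5%.

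| Gap | Too wide by | True level | Part C four-strain NI | Part C A-strain superiority | Part B A-strain superiority |
|---|---|---|---|---|---|
| 0 | 0 | 0.025 | 93.3% both | 43.7% both | 63.9% both |
| 10 pts | 0.4–0.5% | 0.024–0.025 | +0.13 to 0.16 pts | +0.4 to 0.5 pts | +0.4 pts |
| 20 pts | 1.7–2.1% | 0.023 | +0.50 to 0.58 pts | 43.6% → 45.2–45.5% | 64.2% → 65.7–66.0% |
| 30 pts | 4.0–5.0% | 0.020–0.021 | +1.00 to 1.14 pts | 43.4% → 47.2–47.9% | 64.5–64.6% → 68.0–68.8% |

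Part B four-strain noninferiority gains at most 0.3 points. Unstratified noninferiority power never falls below the stated 98% and 93%; in Part C it rises to 94.6–94.8% at a 30-point gap.

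**3. Simulation check.** Unstratified and Mantel-Haenszel-weighted stratified Miettinen-Nurminen score tests were compared with the three-level factor, using 400,000 trials per strain scenario. With no gap, both gave 98.3–98.4% (Part B) and 93.4–93.6% (Part C). Part C moved from 94.1–94.2% to 94.5–94.7% at 20 points, and from 94.8–95.0% to 95.7–96.0% at 30 points. The stratified test held its level at 0.024–0.026 in Part C, including with a 10% stratum of about 128 per arm.

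**The case against.** The unstratified interval is a valid, reproducible method, stated consistently in both documents, and the sample-size figures match it. Adjusting a log-titre ANCOVA while leaving a risk difference unstratified is not a contradiction. No planned power is lost; the loss is only relative to a better interval, and nothing in the documents favours a 20–30-point gap over 0–10. The superiority gains above are for a single test, whereas SCR superiority is reached only after all eight noninferiority endpoints and then GMT superiority succeed. The change needs a protocol amendment, and Part B would then analyse SCR differently from Part A against the same comparator. For noninferiority, a slightly conservative interval is a defensible choice.

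Most of this stands as a limit on size. The effect is conditional, small for noninferiority, and does not inflate type I error; the superiority gains are upper limits on the gain in a claimable result, and the four-strain figures assume independence. It does not remove the main point. The sponsor chose this factor for randomisation and for the GMT model, the documents give no reason for leaving it out of SCR, and the stratified interval is a valid alternative that needs no new data.

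**Conclusion.** The point holds. In Parts B and C every SCR interval is specified without the randomisation strata. The consequence is conservatism and forgone efficiency, not bias or inflated error. There is no effect if SCR is equal across strata. Under the assumed shares and a common gap of 10–30 points, the forgone power is about 0.1–1.1 points for Part C four-strain noninferiority, at most 0.3 points for Part B, and about 0.4–4.6 points for a single A-strain superiority test. It is worth correcting because SCR limits both parts. Confidence in the size is moderate, since the stratum rates and shares are unknown.

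**What to change.** For Parts B and C only, before they are unblinded:

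1. In SAP 3.5.3.1, 3.5.3.4, 4.5.3.1 and 4.5.3.4, specify the Miettinen-Nurminen interval stratified by the three-level randomisation factor, with weights fixed in advance, for example Mantel-Haenszel n1k·n0k/(n1k + n0k). Section 4.5.3.4 currently lists only the A-strain GMT test and a cross-reference, so the SCR test needs to be named there.
2. Fix a pooling rule, for example merging the P302 stratum with the other previously vaccinated participants if it holds under 10% of the PP Immunogenicity Set. SAP 3.5.3.3 already uses that threshold for subgroups.
3. Keep the unstratified interval as a supplementary analysis.
4. Make matching edits in Protocol 3.9.5.1 and 4.9.5.1 and in SAP Tables 18 and 19.

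If the sponsor prefers the unstratified interval, the SAP should say so explicitly. The Part A SCR method should stay as it is: its primary results were reported in the rationale for Amendment 1, before SAP version 2.0.

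The cost is a protocol amendment, which Protocol 2.9 requires when a method for a primary hypothesis changes before unblinding, with whatever approvals Appendix 1 attaches to it, plus edits to four SAP sections and two tables. No new data are needed.

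Separately, Table 17 lists only age group as the stratification covariate in the Part A ANCOVA, while SAP 2.5.3.1 refers to the stratification factors, which in Part A are age and vaccine status (SAP 2.3.4). The two should be reconciled to state the model actually run.

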2.5.3.2. Supplementary Analysis

The primary analyses will be repeated using the Immunogenicity Set as a supplementary analysis.

2.5.3.3. Subgroup Analysis

To assess the consistency of immunogenicity response of mRNA-1010 across subgroups, subgroup analysis of the co-primary endpoints may be conducted by subgroups defined by age group 1, age group 2, previous year's flu vaccine status, race, sex, and BMI category (see Table 5), based on PP Immunogenicity Set. For each subgroup category, the co-primary immunogenicity endpoints will be analyzed using the same statistical methods as for primary analysis. Additional details are documented in Section 2.5.3.1.

If the number of participants in a subgroup is less than 10% of sample size in the analysis set, it may be combined with other subgroups for the subgroup analyses.

2.5.3.4. Analysis of Secondary Endpoints

• The proportion of participants with HAI titer \geq 1:40 at Day 29

The number and percentage of participants with a HAI titer ≥1:40 post-vaccination will be provided with 2-sided 95% CI using the Clopper-Pearson method.

• GMFR comparing Day 29 to Day 1 (Baseline) as measure by HAI

The GMFR will be calculated using the following formula:

$$GMFR=2\left\{\frac{\sum_{i=1}^{n}\log_2\binom{t_{ij}}{t_{ik}}}{n}\right\}=2\left\{\frac{\sum_{i=1}^{n}\log_2(t_{ij})-\log_2(t_{ik})}{n}\right\}$$

where, for n participants, and t_{ij} and t_{ik} are the observed immunogenicity titers for participant *i* at time points *j* and *k*, $j \neq k$.

Descriptive statistics (n, median, min, max) will be provided for the GMFR of HAI titers with corresponding 95% CI at Day 29 over baseline. The 95% CIs will be calculated based on the t-distribution of the log-transformed values then back transformed to the original scale for presentation. In addition, the GMFR with corresponding 95% CI will be plotted at Day 29.

2.5.3.5. Analysis of Exploratory Endpoints

• GMT at Day 181 as measured by HAI

ModernaTX, Inc. mRNA-1010-P303

Descriptive statistics (n, median, min, max) will be provided for the GMT of HAI titers with corresponding 95% CI at Day 181. The 95% CIs will be calculated based on the t-distribution of the log-transformed values then back transformed to the original scale for presentation.

• Proportion of participants reaching seroconversion at Day 181 as measured by HAI

The number and percentage of participants with seroconversion at Day 181 will be provided with 2-sided 95% CI using the Clopper-Pearson method.

For GMT and seroconversion at Day 181, the analyses will be based on participants in PP Immunogenicity Set who also had immunogenicity sample(s) collected between Day 167 and Day 195 (i.e., between -/+ 14 days of Day 181).

- GMT and GMFR of nAbs by assays such as MN assays or alternative methods against vaccine-matched or vaccine-mismatched strains on Day 29 compared with Day 1 (Baseline)
- GMT and GMFR of anti-HA antibodies as measured by HAI against vaccine mismatched strains on Day 29 compared with Day 1 (Baseline).

Descriptive statistics (n, median, min, max) will be provided for these endpoints with corresponding 95% CI at each time point. The 95% CIs will be calculated based on the t distribution of the log-transformed values then back transformed to the original scale for presentation. In addition, the GMT and GMFR with corresponding 95% CI will be plotted at each time point respectively.

• Assessment of immune responses in participants with RT-PCR-confirmed protocoldefined ILI.

A protocol-defined ILI is determined by the occurrence of at least 1 respiratory illness symptom concurrently with at least 1 systemic symptom, or the occurrence of any 2 or more respiratory symptoms, as shown in Table 6.

An RT-PCR confirmed protocol-defined ILI is defined as a positive influenza result on a respiratory sample by RT-PCR performed at the Global Central Laboratory and/or a local

certified laboratory within 7 days of onset of protocol-defined ILI at any time during the study period.

Respiratory symptoms	Systemic symptoms
Sore throat	Body temperature ≥37.5°C [≥99.5°F]
Cough/rhinorrhea/nasal congestion (≥1 of	Chills
the 3 symptoms count as 1 respiratory	Tiredness
symptom)	Headache
Sputum production	Myalgia
Wheezing	Nausea/vomiting
Difficulty breathing	Diarrhea

Table 6 Respiratory and Systemic Symptoms for Protocol-defined ILI (Part A)

CCI	
	_

CCI

Descriptive statistics (n, median, min, max) may be provided for GMT with corresponding 95% CI at each time point for participants with RT-PCR-confirmed protocol-defined ILI. Additionally, the number and percentage of participants with seroconversion at each time point may be provided with 2-sided 95% CI using the Clopper-Pearson method for participants with RT-PCR-confirmed protocol-defined ILI.

